6.3.2 Dose-limiting toxicity (DLT)

For all Phase I cohorts the DLT assessment period will encompass the treatment cycles of the first two consecutive BNT321 doses. Practically, this is 28 days within treatment Cycles 2 and 3.

To be considered a DLT, an AE must meet the following three criteria:

- Occurs during the DLT assessment period of BNT321.
- Is considered BNT321-related (i.e., definitely related or possibly related).
- Occurs in the presence of adequate supportive care (e.g., Grade 3 vomiting despite use of an appropriate anti-emetic regimen).

In addition, to be considered a DLT, an AE must meet at least one of the criteria listed below using CTCAE v5.0 criteria.

- Grade 4 hematologic toxicity (except for: Grade 4 thrombocytopenia without bleeding).
- Grade 3 or higher febrile neutropenia (i.e., ANC <1.0 × 10⁹ cells/L with a single temperature of >38.3°C [>100.9 F] or a sustained temperature of ≥38°C [≥100.4 F] for more than 1 h).
- Grade 3 thrombocytopenia associated with bleeding requiring platelet transfusion.
- Grade 3 microangiopathic hemolytic anemia.
- Grade 3 or higher non-hematologic toxicity (except for: Grade 3 peripheral neuropathy <14 days, Grade 3 fatigue for <7 days, Grade 3 AST or ALT for <14 days, Grade 3 total bilirubin for <72 hrs and not associated with Grade 3 or higher AST or ALT).
- Total bilirubin ≥2 x ULN for >14 consecutive days.
- Grade 2 total bilirubin in association with a Grade 3 or higher ALT or AST (also requires discontinuation of BNT321).
- · Grade 2 or higher hemolysis.
- Delay for >14 consecutive days in administration of the second cycle of BNT321 secondary to liver toxicity (i.e., persistent elevations for this time period of serum transaminase and/or bilirubin).

Patients who will not be able to fulfill the criteria for the DLT assessment will be replaced (this only applies to patients who do not experience a DLT). Replaced patients can continue with BNT321 treatment and follow the same trial procedures except for DLT assessment until they meet the protocol-defined treatment discontinuation criteria.

Page 63 of 127 Version: 2.0 Date: 22 JAN 2024

The SRC will have the option of declaring other toxicities not listed above as DLT. These include sequalae (e.g., encephalopathy) considered related to AST or ALT elevations even if such elevations do not meet the Grade criteria stated above.

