6.3.1.1 BNT321 dose delay or reduction (for BNT321-related events)

Prior to administration of all subsequent doses of BNT321, any clinically significant, BNT321 related, toxicity resulting from prior BNT321 administration must return to ≤ Grade 1 or baseline.

In the event that the administration of BNT321 was delayed for second incidence of Grade 2 or first incidence of Grade ≥3 BNT321-related toxicity, the patient may receive

Page 57 of 127 Version: 2.0 Date: 22 JAN 2024

subsequent administrations of BNT321 at a dose no more than 50% of the current dose. See Table 8 for specific dose modification guidelines for liver function tests (LFTs).

In the event that a clinically significant BNT321-related toxicity necessitates a delay of more than 14 consecutive days, the patient may be removed from trial treatment phase.

Re-escalation of BNT321 dose is not allowed for patients that previously have been dose reduced.

First occurrence of BNT321 related AE Grade ≥3 fulfilling DLT criteria:

- As a first measure, administration of BNT321 needs to be held.
- Investigator must contact the sponsor to discuss whether the patient should be withdrawn from BNT321 treatment or if the next dose should be delayed.
- Administration of BNT321 can be delayed for up to 14 days unless otherwise approved by the sponsor Medical Monitor. If the intensity of AEs resolves to Grade ≤1 within this period, retreatment may be considered under the following:
 - BNT321 should be administered at a dose of no more than 50% and after discussion with sponsor.

Second occurrence of an identical AE Grade ≥3 after re-exposure to BNT321:

- If retreatment leads to an identical AE with same intensity, the next administration of BNT321 should be stopped.
- Retreatment may only be considered on a case-by-case basis after review by the SRC.
- BNT321 must be permanently discontinued if the patient experiences an AE fulfilling the DLT criteria (after the DLT period has ended for the dose escalation) that fails to resolve to Grade ≤1 within 14 d after the planned dosing date, unless otherwise approved by the sponsor Medical Monitor.

Re-escalation of BNT321 dose is not allowed for patients that previously have been dose reduced.

The investigators are encouraged to contact sponsor in case of any safety concern that requires additional discussion or clarification.

BioNTech SE Confidential Page 58 of 127 Version: 2.0 Date: 22 JAN 2024

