Table 8: BNT321 dose modifications: elevated bilirubin and/or transaminases

	Cycle delay	BNT321 Dose reduction/modification
Grade 1 bilirubin, ALT, or AST	No delay	None
Grade 2 bilirubin alone	Delay treatment until recovery Grade <1 (14 days maximum)	1st episode: 50%-100% redose If no recovery to Grade ≤1 in this time frame discontinue BNT321 and DLT should be reported per Section 6.3.2. 2nd episode: reduce dose to 50% 3rd episode: discontinue
Bilirubin >2 x ULN and ALT or AST >3 x ULN	Evaluate for Hy's criteria see liver safety evaluation per Section 10.6	If meets Hy's law and deemed to be related to BNT321 discontinue and do not redose. If determined to be unrelated to BNT321 restart at 50–100% dose, following recovery to Grade ≤1.
Grade 2 bilirubin and Grade <2 ALT/AST (not meeting Hy's law criteria per Section 10.6)	Delay treatment until recovery Grade <1 (14 days maximum)	1 st episode: 1 st episode: 50%–100% redose If no recovery to Grade ≤1 in this time frame discontinue BNT321 and DLT should be reported per Section 6.3.2. 2 nd episode: reduce dose to 50% 3 rd episode: discontinue
Grade 2 bilirubin and Grade 3 AST or ALT (not meeting Hy's criteria per Section 10.6)	Delay treatment until recovery Grade ≤ 1 (14 days maximum)	1 st episode: If recovery to Grade ≤1 within 14 days dose reduction by 50%. If no recovery to Grade ≤1 within this time frame discontinue BNT321 and report DLT per Section 6.3.2. 2 nd episode: discontinue BNT321
Grade 2 ALT or AST with normal bilirubin	Delay treatment until recovery Grade < 1 (14 days maximum)	1 st episode: 50%-100% redose If no recovery to Grade ≤1 in this time frame discontinue BNT321 2 nd episode: reduce dose to 50% 3 rd episode: discontinue
Grade 3 ALT or AST with normal bilirubin	Delay treatment until recovery Grade <1 (14 days maximum)	1 st episode: If recovery to Grade ≤1 within 14 days dose reduction by 50% If no recovery to Grade ≤1 within this time frame discontinue BNT321 and report DLT per Section 6.3.2. 2 nd episode: discontinue BNT321
Grade 3 bilirubin	Delay treatment until recovery Grade ≤ 1 1 (14 days maximum)	1 st episode: If recovery within 14 days dose reduction by 50%; If no recovery to Grade ≤1 within this time period discontinue BNT321 and report DLT per Section 6.3.2. 2 nd episode: discontinue BNT321

Page 59 of 127 Version: 2.0 Date: 22 JAN 2024

	Cycle delay	BNT321 Dose reduction/modification

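### For Grade 2 bilirubin with Grade 3 ALT/AST, Section 6.3.2 requires BNT321 to be stopped, but Table 8 re-doses a recovered first episode at 50%

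*Combined protocol and SAP*

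**What the plan says.** Section 6.3.2 applies to BNT321-related events in the Phase I DLT window, of which it says "Practically, this is 28 days within treatment Cycles 2 and 3". Two of its criteria matter here.

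- The combined liver event: "Grade 2 total bilirubin in association with a Grade 3 or higher ALT or AST (also requires discontinuation of BNT321". There is no minimum duration and no allowance for recovery.
- Grade 3 or higher non-hematologic toxicity, from which it exempts "Grade 3 total bilirubin for <72 hrs and not associated with Grade 3 or higher AST or ALT".

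Table 8 in Section 6.3.1.1 gives the dose changes for liver tests. For a first episode of Grade 2 bilirubin with Grade 3 AST or ALT, not meeting Hy's criteria, it says "If recovery to Grade ≤1 within 14 days dose reduction by 50%. If no recovery to Grade ≤1 within this time frame discontinue BNT321", and it attaches the DLT report to that second branch. A second episode means discontinuation. For a first episode of Grade 3 bilirubin it says "If recovery within 14 days dose reduction by 50%; If no recovery to Grade ≤1 within this time period discontinue BNT321 and report DLT".

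Retreatment is also covered in general terms. For a first related Grade 3 or higher event that meets DLT criteria, Section 6.3.1.1 says "Investigator must contact the sponsor to discuss whether the patient should be withdrawn from BNT321 treatment or if the next dose should be delayed". If the event resolves in time, "BNT321 should be administered at a dose of no more than 50% and after discussion with sponsor". Section 6.3.3 allows treatment after a DLT that has resolved, is not expected to recur, and where the investigator and sponsor judge continuation to be in the patient's interest.

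**The concern.** Liver toxicity is an identified risk of BNT321, and the combined bilirubin and transaminase rule is one of the plan's hepatic stopping rules. A site that follows Table 8 for this event would re-dose a patient for whom Section 6.3.2 requires the drug to be stopped. A site that follows Section 6.3.2 would withhold drug that Table 8 permits.

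The event is plausible in this population. Section 2.3.2 reports DLTs in three of the 15 patients given the combination in the metastatic setting, and all three were hepatic. One had Grade 2 bilirubin with Grade 4 ALT and Grade 3 AST. That patient would stop under Table 8's Grade 4 row and so is not an instance of the conflict, but the case shows that bilirubin and transaminases can rise together on this combination.

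DLTs are also a Phase I primary endpoint and the input to the 3+3 rule in Section 4.1.5, so the prompts that lead a site to report them should match the definition.

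**Working it through.** The check compares texts. The plan gives no figure to reproduce, and no event rate is assumed.

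**Step 1: set the rules side by side, for a BNT321-related first episode in the DLT window.**

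| Event | Section 6.3.2 | Table 8 | Agree? |
|---|---|---|---|
| Grade 2 bilirubin + Grade 3 AST/ALT, not Hy's law | DLT on occurrence; discontinue | Hold up to 14 days; 50% dose if recovered; discontinue and report DLT if not | No, on treatment and on the report prompt |
| Grade 3 bilirubin alone | DLT unless shorter than 72 h | 50% dose if recovered in 14 days; discontinue and report DLT if not | No, on the report prompt |
| Grade 3 AST/ALT, normal bilirubin | Exempt if shorter than 14 days | DLT report if not recovered in 14 days | Yes |
| Any Grade 4 AST, ALT or bilirubin | DLT | Discontinue; report related event as DLT | Yes |

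The 14-day prompt fits isolated Grade 3 transaminases, where Section 6.3.2 has a matching exemption. It does not fit the first two rows.

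**Step 2: does any text settle the treatment conflict?**

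- Section 6.3.2 has nine DLT criteria, and only this one carries a discontinuation note. Section 6.3.3 already covers every DLT. If its general permission to retreat overrode the note, the note would have no effect.
- Discontinuation does not plainly mean a temporary hold. Table 8 uses separate terms for delaying and discontinuing, and Section 6.3.1.1 speaks of holding and delaying.
- Three places lead sites to the permissive text. Table 5 cites 6.3.1.1 and 10.6 for liver-related discontinuation, Section 7.1.1 cites 6.3.1, and Section 6.3.1.1 itself names Table 8. None is a precedence rule, and none mentions the note in 6.3.2.

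**Step 3: bound the conflict.**

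- Table 8's Hy's law row covers bilirubin above 2 x ULN with ALT or AST above 3 x ULN. If such a case meets Hy's law and is "deemed to be related to BNT321 discontinue and do not redose" applies, so both texts stop. The documents do not give the CTCAE cut-offs. Assuming that Grade 3 transaminases lie above 3 x ULN, what remains is mainly Grade 2 bilirubin up to 2 x ULN.
- Grade 4 transaminases, second episodes and failure to recover all lead to discontinuation in Table 8.
- Outside the Phase I window the DLT definition does not apply, and Table 8 stands alone.

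**Step 4: timing of the report prompt.**

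- Combined event: 14 days − 0 = 14 days later than Section 6.3.2.
- Isolated Grade 3 bilirubin: 14 days − 72 h (3 days) = 11 days later.
- Share of the nominal window: 14/28 = 50%. For onset on window day d, the prompt falls after the window when d + 14 > 28, that is, d > 14.
- Other rules act sooner. Section 10.4.4 requires a DLT to be reported within 24 h of first knowledge. Section 8.4.8 makes related Grade 3 or higher AST/ALT, or Grade 2 or higher bilirubin, lasting at least 7 days an event of special interest on the same clock. A persisting event should therefore reach the sponsor by about day 7 + 1 = 8, which is 14 − 8 = 6 days before the Table 8 prompt.

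**The case against.** The strongest reply on treatment is that the parenthesis in Section 6.3.2 is the outlier. Table 8, the general text of 6.3.1.1 and Section 6.3.3 all allow reduced-dose retreatment after recovery, the plan's pointers lead to Section 6.3.1, and sponsor contact is required for a first related Grade 3 or higher event that meets DLT criteria. This shows that re-dosing may be what was intended. It does not remove the contradiction, because the specific note still says stop, and a conversation with the sponsor does not tell either party which rule applies.

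On narrowness the reply is right. The conflict needs Phase I, the DLT window, relatedness, a first episode, Grade 3 but not Grade 4 transaminases, mainly bilirubin up to 2 x ULN, and recovery within 14 days.

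On the DLT prompt the reply largely stands. Table 8 is a dose-modification table that refers back to Section 6.3.2 and nowhere says that a recovered event is not a DLT. Failure to recover can be read as an additional trigger, since 6.3.2 has its own criteria for bilirubin at or above 2 x ULN lasting more than 14 days and for a liver-related delay of more than 14 days in the second BNT321 cycle.

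A reader might infer that Table 8 redefines DLTs, so that recovered events go uncounted and the 3+3 rule clears too high a dose. The documents do not support this. DLT status depends on the event occurring in the window, not on when it is reported. The DLT Evaluation Set in Section 9.4 includes anyone who has a DLT after at least one dose of BNT321, whatever the later recovery or dosing. Under the written rules the 3+3 input is the same whichever re-dosing text is followed.

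**Conclusion.** The treatment conflict is real and literal. For a BNT321-related first episode of Grade 2 bilirubin with Grade 3 AST/ALT in the Phase I DLT window, not meeting Hy's criteria and recovered within 14 days, Section 6.3.2 requires discontinuation and Table 8 re-doses at 50%. Nothing in the plan decides between them. Few patients can be affected, as Phase I has about 20, but this is a stopping rule for a known hepatic risk and should be corrected.

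The reporting point is secondary. In two Table 8 rows the only DLT prompt comes 14 and 11 days later than Section 6.3.2 implies. That is a misleading prompt and not a second definition; if the 24-hour rule is followed, the delay does not arise. No effect on the 3+3 decision is shown, and the documents give no basis for estimating one. The conclusion rests on reading discontinuation in its ordinary sense, as Table 8 itself uses the word.

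**What to change.** 1. In Table 8, change the row for Grade 2 bilirubin with Grade 3 AST or ALT to: discontinue BNT321 and report DLT, when the event is BNT321-related and in the DLT window.
2. Except this event from the retreatment text in Sections 6.3.1.1 and 6.3.3.
3. Add a note to Table 8: *DLT status is set solely by Section 6.3.2, regardless of recovery or re-dosing.* This also deals with the 14-day prompt in the Grade 3 bilirubin row.

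Only if the sponsor confirms that 50% re-dosing is intended should items 1 and 2 be replaced by deleting the parenthesis in Section 6.3.2. The note in item 3 is needed either way.

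The cost is wording in one table row, one note and two retreatment passages, with no extra patients, visits or procedures. The downside is small: a few Phase I patients who recover would not be re-dosed.

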Any event of Grade 4 ALT, AST, or bilirubin	Discontinue treatment	Discontinue BNT321 and report any related event as DLT per Section 6.3.2.

Abbreviations: ALT = alanine aminotransferase, ALT = alanine aminotransferase, DLT = dose-limiting toxicity, ULN = upper limit of normal.

For total bilirubin elevation dose modifications for irinotecan may be also indicated see Section 6.3.1.2.

For AEs occurring in combination part of trial (mFOLFIRINOX + BNT321) which are considered clearly not related to BNT321 but related to the mFOLFIRINOX and require delay or discontinuation of the mFOLFIRINOX regimen, continuation of BNT321 administration as monotherapy is permitted after the AE has resolved to Grade ≤ 1 or baseline.

6.3.1.2 mFOLFIRINOX dose delay or reduction

In case a dose reduction is necessary, the reduced dosage will be maintained until the end of treatment.

In case of recurrent Grade 4 toxicity despite dose reduction, the investigator and the sponsor may discuss the possibility of stopping the treatment.

Table 9: Hematological toxicity based on Day 1 ANC and platelet count

	Cycle delay	Dose reduction		
		Irinotecan	Oxaliplatin	5-FU/leucovorin
Neutrophils <1.5 x 10 ⁹ /L	Delay treatment until	1 st episode: dose reduction to 120 mg/m ²	1 st episode: no dose reduction	1 st episode: no dose reduction
	neutrophils are ≥1.5 x 10 ⁹ /L	2 nd episode: maintain dose at 120 mg/m ²	2 nd episode: reduce dose to 60 mg/m ²	2 nd episode: no dose reduction
	and resume cycle with G-CSF*	3 rd episode: discuss treatment stop or maintain only LV/5-FU	3 rd episode: discuss treatment stop or maintain only LV/5-FU	
Platelets <100 x 10 ⁹ /L	Delay treatment until recovery	1 st episode: no reduction in dose	1 st episode: reduce dose to 60 mg/m ²	1 st episode: no dose reduction
	(platelets ≥100 x 10 ⁹ /L)	2 nd episode: reduce dose to 120 mg/m ²	2 nd episode: maintain dose at 60 mg/m²	2 nd episode: reduce the dose of IV continuous infusion
		3 rd episode: discuss withholding irinotecan*	3 rd episode: discuss withholding oxaliplatin*	by 25%
				3 rd episode: discuss withholding 5-FU

Page 60 of 127 Version: 2.0 Date: 22 JAN 2024

*Granulocyte colony stimulating factor and other hematopoietic growth factors may be used in the management of acute toxicity (such as febrile neutropenia) or prophylactically, when clinically indicated at the investigator's discretion. Blood cell transfusion (RBC or platelet) is allowed if clinically indicated. See Section 6.9.2 for more information.

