6.3.3 Retreatment of patients experiencing DLT

Patients experiencing DLT during the DLT assessment period will not receive additional trial treatment unless all the following conditions are met:

- The DLT has resolved to at least Grade 1 or returned to baseline with appropriate treatment (e.g., anti-emetics) or with a delay in trial treatment dosing.
- The DLT is not expected to recur based on an intervention such as prophylactic use of appropriate treatment (e.g., prophylactic anti-emetics), or dose reduction.
- Continued administration of trial treatment is considered to be in the patient's best interest based on the opinion of the investigator and the sponsor.

For the combination mFOLFIRINOX + BNT321, if a DLT is considered clearly related to a specific drug, the patient may continue with the remaining trial treatment if considered in the patient's best interest by the investigator and the sponsor.

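### For one BNT321-related liver event in the Phase I DLT window, Section 6.3.2 stops BNT321 and Table 8 allows redosing at half dose, with no rule on which prevails

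*Combined protocol and SAP*

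**What the plan says.** Section 6.3.2 sets the DLT criteria for Phase I. An event must fall in the assessment window (28 days within Cycles 2 and 3), be definitely or possibly related to BNT321, occur despite adequate supportive care, and meet at least one of nine criteria. One of these is "Grade 2 total bilirubin in association with a Grade 3 or higher ALT or AST (also requires discontinuation of BNT321"). It is the only one of the nine that carries a dosing order.

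Table 8 in Section 6.3.1.1 gives the dose changes for raised bilirubin and transaminases. Its row for Grade 2 bilirubin with Grade 3 AST or ALT, limited to cases not meeting Hy's criteria, allows a delay of at most 14 days. For a first episode it then says: "If recovery to Grade ≤1 within 14 days dose reduction by 50%. If no recovery to Grade ≤1 within this time frame discontinue BNT321". In the latter case the row also asks for a DLT report. A second episode means discontinuation.

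Two other Table 8 rows are relevant. For bilirubin above 2 x ULN with ALT or AST above 3 x ULN: "If meets Hy's law and deemed to be related to BNT321 discontinue and do not redose". For any Grade 4 ALT, AST or bilirubin: "Discontinue BNT321 and report any related event as DLT per Section 6.3.2".

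Two general texts deal with retreatment. For a first related AE of Grade 3 or higher that meets DLT criteria, Section 6.3.1.1 requires BNT321 to be held and the sponsor contacted. If the event resolves in time and retreatment is considered, "BNT321 should be administered at a dose of no more than 50% and after discussion with sponsor". Section 6.3.3 says: "Patients experiencing DLT during the DLT assessment period will not receive additional trial treatment unless all the following conditions are met". The three conditions are resolution, no expected recurrence given an intervention, and the patient's best interest in the opinion of investigator and sponsor.

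**The concern.** For the same event, one section orders the drug stopped and the other describes how to restart it. A site or medical monitor following either text departs from the other.

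The organ makes this worth settling. Section 2.3.2 reports three DLTs among 15 patients given this combination in the metastatic setting, all of them liver events, and Section 4.2.1 leaves open doses above the metastatic maximum tolerated dose. Table 5 and the liver item in Section 7.1.1 send the reader to 6.3.1.1 and 6.3.1 for stopping on liver function, which leads to Table 8 and its redose. The stop in 6.3.2 sits in a list whose main purpose is to define DLTs. At stake is whether a patient with combined bilirubin and transaminase elevation attributed to BNT321 is exposed to it again.

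**Working it through.** No sample size, power or error rate is involved, so the check is a comparison of texts.

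**Step 1. The event.** Phase I, inside the DLT window; Grade 2 bilirubin with Grade 3 ALT or AST; at least possibly related to BNT321; not meeting Hy's criteria; first episode.

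**Step 2. The instructions side by side.**

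| Source | Dosing instruction | Effect of recovery to Grade 1 or less |
|---|---|---|
| Section 6.3.2 | Discontinue BNT321 | None stated |
| Table 8, matching row | Delay, at most 14 days | Resume at 50%; discontinue only without recovery or at a second episode |
| Section 6.3.1.1, general text | Hold and contact sponsor | Retreatment may be considered at no more than 50% |
| Section 6.3.3 | No further treatment by default | Retreatment if all three conditions hold |

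**Step 3. Does Table 8 apply inside the window?** Yes. Section 6.3.1.1 refers liver-test cases to it without excluding the window, and the row itself mentions reporting a DLT under 6.3.2.

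**Step 4. Worked case.** In Cycle 2 a patient has related Grade 2 bilirubin and Grade 3 ALT, does not meet Hy's criteria, and recovers to Grade 1 or less by day 10. Under 6.3.2 BNT321 is stopped. Under Table 8, after the hold and sponsor contact, it resumes at 50%.

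**Step 5. How much is left in conflict?**
- Any Grade 4 ALT or AST is outside it, because Table 8 also discontinues.
- Related cases meeting Hy's law are outside it, because Table 8 discontinues without redosing.
- What remains is mainly bilirubin at or below 2 x ULN, which cannot enter the Hy's-law row. This assumes that Grade 2 bilirubin can occur at or below 2 x ULN; the protocol does not print the CTCAE cut-offs. A smaller remainder is bilirubin above 2 x ULN where Hy's law is not met but BNT321 is still thought possibly responsible.

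**Step 6. Earlier experience (Section 2.3.2).** Of the three DLTs in 15 patients, two had Grade 4 ALT and are outside the conflict: 3 − 2 = 1 left. That patient had Grade 3 ALT and AST with raised total bilirubin. The text does not clearly give the bilirubin grade and does not say whether Hy's criteria were met. So 0 or 1 of the 15 fell in the gap (0%, or 1/15 = 6.7%), and the documents do not show which. Grade 3 or higher AST occurred in 40% (0.40 x 15 = 6 patients) and ALT in 26.7% (0.267 x 15 = 4 patients). How often either coincided with Grade 2 bilirubin is not reported.

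**The case against.** The best defence is that the texts can be read together. Section 6.3.2 does not say permanent discontinuation, whereas other places do say permanently or forbid redosing. Section 6.3.3 follows directly and offers a route back after any DLT, without excepting this criterion. The hold and sponsor contact in 6.3.1.1 put the choice before the sponsor in any case.

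Part of this stands. A reader might infer that a site may redose from Table 8 on its own authority. The documents do not support that: the event is a related AE of Grade 3 or higher meeting DLT criteria, so both safeguards apply. The reconciliation itself does not stand. If 6.3.3 governed this event like every other DLT, the parenthesis would add nothing, yet it was attached to one criterion of nine. Table 8 also sets delay against discontinue, so reading discontinuation as a hold is strained.

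A reader might also infer a second contradiction, over DLT reporting. Table 8 ties the report to non-recovery here and again for Grade 3 bilirubin ("If recovery within 14 days dose reduction by 50%; If no recovery to Grade ≤1 within this time period discontinue BNT321 and report DLT"), while 6.3.2 excepts only "Grade 3 total bilirubin for <72 hrs and not associated with Grade 3 or higher AST or ALT". But both rows point to 6.3.2, and neither says a recovered event is not a DLT, so 6.3.2 probably governs. The cue is misleading rather than contradictory. Nor can a reporting delay be calculated from it: Table 8 gives its 14 days as a cycle delay, and 6.3.1.1 in one place counts from the planned dosing date, so the clock need not start at onset. Related Grade 3 or higher AST or ALT, or Grade 2 or higher bilirubin, lasting at least 7 days is also an event of special interest reported on SAE timelines (Section 8.4.8), and the safety review committee sees data by patient and cohort (Section 10.1.5).

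Finally, the three earlier liver DLTs might suggest a common problem. Two are outside the conflict and the third cannot be placed.

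**Conclusion.** The concern holds in a narrow form. For a BNT321-related event of Grade 2 bilirubin with Grade 3 ALT or AST in the Phase I DLT window, not meeting Hy's criteria, Section 6.3.2 requires discontinuation, Table 8 provides for a half-dose restart on recovery, and the protocol gives no order of precedence. Sections 6.3.1.1 and 6.3.3 make the restart conditional; they do not cancel the stop.

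It can arise only in a 28-day window among about 20 patients, and no documented earlier case is shown to be an example. Its weight comes from the kind of instruction (stop or re-expose) and the organ concerned, not from frequency. It does not bear on the Phase II sample size, power or primary analysis. The conclusion rests on reading discontinuation as more than a hold and on Table 8 applying inside the window; the wording favours both. The protocol should be corrected, since following one of its rules means breaking another.

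**What to change.** Choose one rule and write it in both places.

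- **If the stop is intended:** in the Table 8 row for Grade 2 bilirubin with Grade 3 AST or ALT, replace the 50% redose with *discontinue BNT321 and report DLT per Section 6.3.2* when the event is BNT321-related and in the DLT window.
- **If redosing is intended:** delete the parenthesis on discontinuation from the criterion in 6.3.2, and make redosing in that Table 8 row subject to the hold and sponsor contact in 6.3.1.1 and to all three conditions in 6.3.3.

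In either case, add one sentence that Section 6.3.2 alone determines whether an event is a DLT, whether or not it recovers. This also removes the misleading reporting cue.

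Do not resolve the matter with a general statement that Table 8 governs dosing. That could override the sponsor contact and the 6.3.3 conditions for other liver DLTs, such as Grade 3 bilirubin lasting beyond 72 hours that then recovers.

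The cost is a wording change in one table row or one criterion with its row, plus one sentence. No patients, visits or analyses are added.

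### For one recovering liver DLT in Phase I, Section 6.3.2 stops BNT321 while Table 8 resumes it at half dose, and no text says which governs

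*Combined protocol and SAP*

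**What the plan says.** Section 6.3.2 defines DLTs for the Phase I cohorts. The window covers the cycles of the first two BNT321 doses, in practice 28 days in Cycles 2 and 3, and the event must be judged definitely or possibly related to BNT321. One criterion reads "Grade 2 total bilirubin in association with a Grade 3 or higher ALT or AST (also requires discontinuation of BNT321". Of the nine criteria listed, only this one carries a dosing order.

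Table 8, in Section 6.3.1.1, has a row for "Grade 2 bilirubin and Grade 3 AST or ALT", limited to cases that do not meet Hy's criteria. Treatment is delayed for up to 14 days. For a first episode the row says "If recovery to Grade ≤1 within 14 days dose reduction by 50" per cent, and then "If no recovery to Grade ≤1 within this time frame discontinue BNT321 and report DLT per Section 6.3.2". A second episode stops the drug. The separate Hy's row says "If meets Hy's law and deemed to be related to BNT321 discontinue and do not redose".

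Three other places bear on the same patient:

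- Section 6.3.1.1, under "First occurrence of BNT321 related AE Grade ≥3 fulfilling DLT criteria", holds BNT321 and requires contact with the sponsor. If the event settles to Grade ≤1 in time, it allows re-treatment at no more than half dose to be considered.
- Section 6.3.3 states "Patients experiencing DLT during the DLT assessment period will not receive additional trial treatment unless all the following conditions are met". The conditions are resolution, no expected recurrence, and a shared view of investigator and sponsor that continuing is in the patient's interest.
- Section 7.1.1 says that stopping for abnormal liver function should be considered under Section 6.3.1. Separately, it lists unacceptable AEs with a pointer to Section 6.3.

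**The concern.** Both instructions are current, unredacted text, and they describe the same patient. One stops BNT321; the other restarts it. What is at stake is whether someone who has just had a combined bilirubin and transaminase DLT is exposed to the antibody again.

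Liver toxicity is the known limit of this combination. Section 2.3.2 reports three patients with DLTs among the 15 treated earlier with mFOLFIRINOX + BNT321, and all three events were hepatic. The sponsor must agree before re-treatment, but would have two contrary written rules to apply.

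A smaller matter is that the Table 8 row mentions DLT reporting only when recovery fails. Section 6.3.2 makes the event a DLT when it occurs, and Section 10.4.4 requires DLTs to be reported within 24 h.

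**Working it through.** No figure in the plan needs reproducing. The check is a comparison of texts, followed by two short calculations of size.

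**Step 1: where the two rules part.** Take a BNT321-related event in Cycles 2 or 3 of Phase I, with Grade 2 bilirubin and the ALT/AST grade shown.

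| Case | Section 6.3.2 | Table 8 | Same dosing order? |
|---|---|---|---|
| Grade 3, non-Hy's, first episode, recovers within 14 days | DLT; discontinue | Delay, then resume at 50%; DLT not mentioned | **No** |
| Grade 3, non-Hy's, first episode, no recovery | DLT; discontinue | Discontinue; report DLT | Yes |
| Grade 3, non-Hy's, second episode | DLT; discontinue | Discontinue | Yes |
| Related Hy's law case | DLT; discontinue | Discontinue, no re-dosing | Yes |
| Grade 4 ALT or AST | DLT; discontinue | Discontinue; report as DLT | Yes |

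Only the first line conflicts.

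**Step 2: could discontinuation mean a temporary hold?** Not comfortably. Table 8 uses delay and discontinue as different actions within the same rows.

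**Step 3: do the general rules settle it?** Sections 6.3.1.1 and 6.3.3 allow conditional re-treatment after DLTs in general. Neither mentions the parenthesis in Section 6.3.2. If the general route applied to this criterion too, the parenthesis would add nothing. Section 7.1.1 points to Section 6.3.1 and, for unacceptable AEs, to Section 6.3 as a whole, which contains both rules.

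**Step 4: does the Table 8 wording fit elsewhere?** Yes. The row for Grade 3 ALT or AST with normal bilirubin uses the same first-episode wording. There it agrees with Section 6.3.2, which exempts Grade 3 AST or ALT lasting less than 14 days. Section 6.3.2 gives no such exemption under the criterion that combines Grade 2 bilirubin with Grade 3 transaminases.

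**Step 5: how often.** Inputs are from Section 2.3.2: 15 combination patients, three with DLTs.

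- Two had Grade 4 ALT, for which Table 8 orders discontinuation outright, so they fall outside the row.
- The third had Grade 3 ALT and AST with a bilirubin elevation whose grade is not clearly stated. It may be Grade 3 bilirubin or a Hy's case, or it may fit the row.

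The count is therefore 0/15 or at most 1/15. Exact (Clopper-Pearson) 95% limits:

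- 0/15: 0% to 1 − 0.025^(1/15) = 21.8%.
- 1/15 = 6.7%: lower limit 1 − 0.975^(1/15) = 0.2%; upper limit 31.9%, the p at which P(X ≤ 1 | n = 15) = 0.025.

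Those patients had metastatic disease and a redacted dose range, so this is not a projection to the adjuvant setting.

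**Step 6: what one patient's treatment turns on.** BNT321 is planned in Cycles 2 to 24, which is 24 − 1 = 23 doses. After a DLT following dose 1 or dose 2, 22 or 21 remain. Section 6.3.2 gives 0 of these. Table 8 gives at most 21 to 22 half-doses, each 0.5 × 0.5 = 0.25 mg/kg at dose level 1. This is a ceiling: it assumes no dose lost to the delay, no second episode and completion of Cycle 24.

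**The case against.** The best defence is that most of the text points one way. Section 6.3.1.1, Section 6.3.3 and Table 8 all allow a reduced dose after recovery, which leaves a single parenthesis as the outlier. That parenthesis also does not say permanent. Table 13 does say so for Grade 3 and 4 infusion reactions, while its Grade 2 row requires discontinuation of administration after a second interruption and still provides for later doses. This has weight, and it is why deleting the parenthesis is a legitimate alternative fix. It does not remove the conflict: the order is attached to this one criterion, and Table 8 itself separates delay from discontinue.

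A reader might infer that a site could re-dose on Table 8 alone. The documents do not support that: Sections 6.3.1.1 and 6.3.3 both involve the sponsor first.

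A reader might also infer that reporting would slip by 14 days. The wording is misleading, but three rules limit the harm: the 24 h rule in Section 10.4.4, the sponsor contact in Section 6.3.1.1, and Section 8.4.8. The last makes a related Grade ≥3 transaminase or Grade ≥2 bilirubin elevation lasting 7 days or more an AESI, reportable on SAE timelines.

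Finally, it is tempting to state the bilirubin range affected by taking the Hy's row as a cap at 2 x ULN. That row only calls for evaluation. Under Section 10.6 a case is confirmed only after other causes are excluded, so an event above that level can return to the non-Hy's row. The Grade 2 lower limit is not printed either. No band should be quoted.

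**Conclusion.** The point holds in a narrow form. For a first, BNT321-related, non-Hy's event of Grade 2 bilirubin with Grade 3 ALT/AST, in the Phase I DLT window and recovering to Grade ≤1 within 14 days, Section 6.3.2 and Table 8 give incompatible orders. Nothing ranks them.

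It is minor. It can arise only among about 20 Phase I patients and in a 28-day window, and sponsor involvement stands between the conflict and any re-dosing. The frequency rests on how the third earlier DLT is read.

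A reader might infer that the 3+3 count, and so the MTD or RP2D, is at risk. The documents do not support that: Section 6.3.2 alone defines a DLT, and the event meets it whether or not it recovers. No effect on the Phase II analysis is claimed.

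**What to change.** (1) In the Table 8 row for Grade 2 bilirubin with Grade 3 AST or ALT (non-Hy's), replace the first-episode text with: *If BNT321-related and within the Phase I DLT assessment period: report as a DLT within 24 h per Sections 6.3.2 and 10.4.4, whether or not it recovers, and discontinue BNT321. Otherwise: if recovery to Grade ≤1 within 14 days, dose reduction by 50%; if not, discontinue BNT321; record the event as an AE meeting DLT criteria (Section 6.3.5).* The last clause keeps a prompt in the row, because the Phase II stopping rule in Section 6.3.5 counts such AEs.

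(2) Add to Section 6.3.3: *BNT321 is not resumed after a DLT for which Section 6.3.2 requires discontinuation.*

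Alternative, if the sponsor intends conditional re-dosing through Section 6.3.3: delete the parenthesis in Section 6.3.2, and still correct Table 8 so that DLT reporting does not depend on failure to recover.

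The cost is one table cell and one sentence in an amendment, with no added visits, procedures or patients. Under the first option a Phase I patient who recovers loses the half-dose choice, and the same toxicity would stop BNT321 in Cycle 3 but allow half dose in Cycle 4. The later-cycle rule is left alone. Section 6.3.1.1 already has a recovery test for that period, for an AE meeting DLT criteria "after the DLT period has ended for the dose escalation) that fails to resolve to Grade ≤1 within 14 d". It is not identical to Table 8: it counts from the planned dosing date and allows Medical Monitor exceptions.
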